## 7.2 Withdrawal of subjects from study

#### 7.2.1 Withdrawal - amended

Subjects will be withdrawn from the study for the following reasons:

- Consent withdrawal
  - At their own request or at the request of their legally acceptable representative
  - At any time during the study and without giving reasons, a subject may decline to participate further. The subject will not suffer any disadvantage as a result.
- Substantial non-compliance with study procedures
  - Subject who is off study drug (BAY 1163877) longer than 8 consecutive days in Cycle 1
  - Subjects lost to follow-up
- Violation of in- / exclusion criteria (subject no longer eligible for the study)
  - If the subject develops conditions which would have prevented his / her entry into the study according to the in- / exclusion criteria, he / she must be withdrawn immediately if safety is concerned; in other cases, the investigator will decide whether there is a conflict with the study objectives.
  - The development of a second malignancy that requires a different treatment.
  - Development of any intercurrent illness or situation which may, in the judgment of the investigator, affect assessments of clinical status and study endpoints to a relevant degree.
  - Subjects with a positive urine beta-HCG test confirming pregnancy. Pregnancy will be reported under the same timelines as a serious adverse event.
- Unacceptable toxicity
  - If, in the investigator's opinion, continuation of study would be harmful to the subject's well-being
  - Severe allergic reactions, such as exfoliate erythrodermia, anaphylaxis, or vascular collapse
  - Any other potential adverse reaction deemed sufficiently serious to warrant discontinuation of treatment by the investigator or his designated associate(s).
  - Use of illicit drugs or other substances that may, in the opinion of the investigator or his designated associate(s), have a reasonable chance of contributing to toxicity

No. BAY 1163877 / 16443

17 Oct 2018 Version 8.0 Page: 54 of 395

or otherwise confound the results.

- Retinal detachment of grade 2 or higher according to CTCAE v4.03 46
- AST/ALT > 3xULN with concomitant bilirubin > 2xULN in the absence of another reason for these elevations
- AST/ALT > 8xULN or AST/ALT > 5xULN for > 2 weeks if no other reason is found for these elevations
- Tumor progression

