#### Liver toxicity

Dose modifications of BAY 1163877 for liver toxicity are presented in Table 8-6. Liver toxicity refers to ALT and / or AST and / or bilirubin increases and / or hepatic failure considered possibly related to BAY 1163877, and graded according to CTCAE v4.03.

No. BAY 1163877 / 16443

17 Oct 2018 Version 8.0 Page: 63 of 395

Table 8-6: Dose modifications of BAY 1163877 for liver toxicity - amended

Toxicity	Modification schedule
Grade 1-2	No modifications. Treat as scheduled and check AST, ALT and bilirubin weekly for at least 4 weeks.
Grade 3	Hold BAY 1163877 until recovery to ≤ grade 2 or baseline, then reduce 1 dose level and check AST, ALT and bilirubin weekly for at least 4 weeks. a
- 1 st reappearance	Hold BAY 1163877 until recovery to ≤ grade 2 or baseline, then reduce 1 additional dose level and check AST, ALT and bilirubin weekly for at least 4 weeks a .
- 2 nd reappearance	Withdraw subject from the study treatment.b
Grade 3 with ALT or AST > 8x ULN and a concomitant rise in bilirubin (of any degree compared to previous bilirubin level) or hepatic failure (of any degree)	In case of a negative risk-benefit assessment, consider permanent discontinuation at the first occurrence b,c OR Hold BAY 1163877 until recovery to ≤ grade 2 or
	baseline, then reduce 1 dose level and check AST, ALT and bilirubin weekly for at least 4 weeks a .
-1st reappearance	Withdraw subject from study treatment.b
Grade 4 b	Withdraw subject from study treatment.b

- a Dose will not be re-escalated after dose reduction for toxicity
- b In case of discontinuation, check AST, ALT, and bilirubin weekly until recovery to baseline or stabilization.
- c Subjects with Gilbert's syndrome who develop elevated transaminases should be managed as per the above outlined recommendations for the respective observed elevation of ALT and / or AST.

Patients with AST/ALT > 3xULN with concomitant bilirubin > 2xULN in the absence of another reason for these elevations have to permanently discontinue study drug. Permanent discontinuation also applies to patients with AST/ALT > 8xULN or AST/ALT > 5xULN for > 2 weeks if no other reason is found for these elevations. 50

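### Table 8-6 directs or permits re-treatment after Grade 3 liver events for which the text below it and Section 7.2.1 require permanent discontinuation

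*Protocol*

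**What the plan says.** Table 8-6 in Section 8.4.3 covers liver toxicity considered possibly related to BAY 1163877 and graded by CTCAE v4.03. It has two Grade 3 rows.

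- **Plain Grade 3 row, first occurrence:** "Hold BAY 1163877 until recovery to ≤ grade 2 or baseline, then reduce 1 dose level and check AST, ALT and bilirubin weekly". The same row calls for withdrawal only at the second reappearance.
- **Severe Grade 3 row:** the label begins "Grade 3 with ALT or AST > 8x ULN and a concomitant rise in bilirubin (of any degree compared to previous bilirubin level" and goes on to include hepatic failure. At first occurrence it offers two alternatives joined by OR. One is "In case of a negative risk-benefit assessment, consider permanent discontinuation at the first occurrence"; the other is the same hold-and-reduce action as in the plain row.

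The paragraph directly under the table is mandatory. Patients with AST/ALT above 3x ULN and bilirubin above 2x ULN "in the absence of another reason for these elevations have to permanently discontinue study drug". It continues: "Permanent discontinuation also applies to patients with AST/ALT > 8xULN or AST/ALT > 5xULN for > 2 weeks if no other reason is found".

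Section 7.2.1 repeats both criteria under the opening "Subjects will be withdrawn from the study for the following reasons". They are "AST/ALT > 3xULN with concomitant bilirubin > 2xULN in the absence of another reason for these elevations" and "AST/ALT > 8xULN or AST/ALT > 5xULN for > 2 weeks if no other reason is found". Footnotes in both sections attribute the liver criteria to Amendment 6.

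**The concern.** The table and the stopping rules give different instructions for the same patient. The rows carry no exception and no reference to the stopping criteria. They are not limited to events with another explanation. Nothing in the protocol text available says that the paragraph or Section 7.2.1 overrides the table.

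This is a matter of patient safety. A dose-modification table is what a site is likely to consult when a result comes in. A site that applies the plain Grade 3 row literally would give a first-in-human drug again, one level lower, after a liver event for which the protocol elsewhere requires withdrawal. The stricter rule is visible in two places, so this is a contradiction to resolve and not a missing safeguard.

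**Working it through.** There is no sample size, power or error rate to reproduce; the check sets the instructions side by side. All cases are drug-related, Grade 3, first occurrence, with no other reason found.

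| Case | Table 8-6 | Paragraph below and 7.2.1 | Conflict |
|---|---|---|---|
| (a) AST/ALT > 8x ULN, no bilirubin rise, no hepatic failure | Plain row: hold, reduce, re-treat | Stop permanently | Yes |
| (b) AST/ALT > 8x ULN with any bilirubin rise | Severe row: stopping optional | Stop permanently | Yes |
| (c) AST/ALT > 3x but not > 8x ULN, bilirubin > 2x ULN | Plain row: hold, reduce, re-treat | Stop permanently | Yes |
| (d) AST/ALT > 5x to 8x ULN for > 2 weeks | Plain row: hold, reduce, re-treat | Stop permanently | Yes, limited in time (below) |
| (e) AST/ALT > 5x to 8x ULN for ≤ 2 weeks, bilirubin ≤ 2x ULN | Plain row: hold, reduce, re-treat | No criterion met | No |

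**Cases (a) and (b)** need no CTCAE cut-off from outside the text. The severe row's label puts AST/ALT above 8x ULN within Grade 3. That row applies only with a bilirubin rise or hepatic failure, so an event above 8x ULN with neither falls on the plain row.

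**Do the general rules of 8.4.3 already prevent re-treatment?** Only in part.

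- After a Cycle 1 DLT, re-treatment is allowed only if the Grade 3 non-hematological toxicity lasts no longer than 7 days. A short event of type (a), (b) or (c) passes that test.
- For drug-related events of Grade 3 or higher, the general text requires recovery to ≤ Grade 1 within 21 days. A transient elevation can meet this. Table 8-6 asks only for ≤ Grade 2 or baseline and sets no time limit.

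**Case (d)** assumes that Grade 3 includes 5x to 8x ULN, since the CTCAE cut-offs are not in the text available. If the general time limits apply alongside the table, and the hold starts when the elevation is first seen, the overlap is the permitted delay minus the 14 days after which the stopping rule applies:

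- Cycle 1, event counted as a DLT: max(0, 7 − 14) = 0 days.
- From Cycle 2: 21 − 14 = 7 days (days 15 to 21), and only if the event reaches ≤ Grade 1 by day 21.

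These counts are conditional. Section 8.4.4 lets the investigator and sponsor discuss whether a laboratory abnormality without a clear clinical correlate is a DLT. If Table 8-6 is read alone, it has no time limit and the 7-day bound does not apply. The finding rests on cases (a) to (c).

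**The case against.** The strongest reply is that this is a general rule followed by an exception. The table sets graded management, and the paragraph closing the same subsection lists patients who must stop regardless. Its wording is imperative, Section 7.2.1 repeats it, and a table footnote and the paragraph carry the same Amendment 6 reference. On that reading a site goes wrong only by ignoring a mandatory paragraph under the table. This is probably the intent. But the protocol text available does not say so, and an explicit OR in the severe row offers a choice that the paragraph forbids for every event above 8x ULN with no other reason found.

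A second reply is that the two texts cover different populations. The table applies to events possibly related to the drug, the stopping rules to events with no other reason found. Where another reason exists but relatedness is not excluded, both rows can operate. So can the plain row for events below every threshold, as in case (e). That is correct, and it limits the finding. It does not remove it, because the rows also cover events with no other reason.

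A third reply concerns case (d): the day counts let the general text of 8.4.3 limit the table, while the contradiction itself depends on the paragraph not doing so. That is fair, so the counts should be read only as a conditional bound. Section 7.2.1 also withdraws subjects off drug for more than 8 consecutive days in Cycle 1, which further narrows re-treatment in that cycle. Cases (a) to (c) do not depend on any of this.

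**Conclusion.** The contradiction is real and stands in the current protocol text. For drug-related Grade 3 liver events at first occurrence with no other reason found:

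- The plain row directs re-treatment where the text requires stopping, both for AST/ALT above 8x ULN without a bilirubin rise or hepatic failure and for AST/ALT above 3x but not above 8x ULN with bilirubin above 2x ULN.
- The severe row makes optional what the text makes mandatory.
- The criterion of more than 5x ULN for more than 2 weeks adds a smaller conflict. Under the general time limits it is nil for a Cycle 1 DLT and at most 7 days from Cycle 2, assuming that Grade 3 includes 5x to 8x ULN.

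No incidence can be given, because the protocol states none. The stricter rule is adjacent and repeated, which lowers the chance of error. Even so, a stated row that would re-expose a subject who must be withdrawn should be corrected.

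**What to change.** In both Grade 3 rows of Table 8-6, require permanent discontinuation at first occurrence when no other reason is found and AST/ALT is > 8x ULN, or > 5x ULN for > 2 weeks, or > 3x ULN with bilirubin > 2x ULN. Limit hold-and-reduce to the remaining Grade 3 events. Add one sentence that the stopping rules in Section 7.2.1 take precedence over every row of Table 8-6.

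The precedence sentence alone would settle the contradiction formally. Changing the rows as well puts the instruction where the site will read it. If a third copy of the thresholds is unwelcome, the rows can point to Section 7.2.1.

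The cost is two table rows and one sentence in the next amendment, with no effect on data or on patients' schedules.

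### For possibly related Grade 3 ALT/AST above 8x ULN with no other reason found, Table 8-6 allows a re-start after the first occurrence, but the text below it and Section 7.2.1 require a permanent stop

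*Protocol*

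**What the plan says.** The subsection on liver toxicity in Section 8.4.3 limits Table 8-6 to transaminase or bilirubin rises and hepatic failure that are "considered possibly related to BAY 1163877, and graded according to CTCAE v4.03".

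- **Plain Grade 3 row.** The first occurrence is handled by "Hold BAY 1163877 until recovery to ≤ grade 2 or baseline, then reduce 1 dose level and check AST, ALT and bilirubin weekly". At the first reappearance the drug is held again, "then reduce 1 additional dose level and check AST, ALT and bilirubin weekly". At the second reappearance the subject is withdrawn from treatment.
- **Row for values above 8x ULN.** It is headed "Grade 3 with ALT or AST > 8x ULN and a concomitant rise in bilirubin (of any degree compared to previous bilirubin level"), and it also names hepatic failure. The first option is "In case of a negative risk-benefit assessment, consider permanent discontinuation at the first occurrence". The alternative is to hold and resume one level lower. At the first reappearance the subject is withdrawn.
- **Paragraph below the table.** Subjects with AST/ALT above 3x ULN and bilirubin above 2x ULN, "in the absence of another reason for these elevations have to permanently discontinue study drug". It continues: "Permanent discontinuation also applies to patients with AST/ALT > 8xULN or AST/ALT > 5xULN for > 2 weeks if no other reason is found".
- **Section 7.2.1.** The same liver criteria appear under unacceptable toxicity, in a list that opens "Subjects will be withdrawn from the study for the following reasons".

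**The concern.** One event receives two instructions. The table lets the site resume at a lower dose after a Grade 3 transaminase rise above 8x ULN. The paragraph below it and Section 7.2.1 do not allow resumption if no other reason is found. The conflict is plainest in the row that itself names values above 8x ULN. There, with bilirubin also rising or hepatic failure present, stopping is only something to consider.

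The issue is subject safety in a first-in-human trial. A site that acts on the table could re-expose a subject with suspected drug-induced liver injury whom the protocol elsewhere requires to stop.

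**Working it through.** No sample size, power or error rate is involved. The check compares the current rules and counts the re-starts each allows.

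**1. Can a value above 8x ULN be Grade 3?** Yes, on the table's own wording, since one row is defined as Grade 3 with ALT or AST above 8x ULN. No outside grading scale is needed.

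**2. Which row applies?** With a concomitant bilirubin rise or hepatic failure, the row for values above 8x ULN applies. Without either, only the plain Grade 3 row fits, because it has no upper limit at 8x ULN.

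**3. Can the table and the mandatory rule apply to the same event?** The table requires possible relatedness; the mandatory rule requires that no other reason is found. Section 9.5.1.2.3 places a clear alternative explanation under a causality answer of no. An event judged related and without another explanation therefore meets both conditions. The two conditions are not identical. Section 7.1.1.2 admits subjects with liver involvement at ALT/AST up to 5x ULN, so a possibly related rise may also have a tumour contribution. In such a case another reason may be found, and the table then applies without conflict.

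**4. Re-starts allowed for possibly related Grade 3 ALT/AST above 8x ULN, no other reason found**

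| Rule | First occurrence | First reappearance | Second reappearance |
|---|---|---|---|
| Plain Grade 3 row | 1 | 1 | 0 (withdraw) |
| Row above 8x ULN, hold option chosen | 1 | 0 (withdraw) | not reached |
| Row above 8x ULN, discontinuation chosen | 0 | not reached | not reached |
| Paragraph below table; Section 7.2.1 | 0 | not reached | not reached |

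Per-subject ceilings are 1 + 1 = 2 for the plain Grade 3 row, 1 + 0 = 1 for the other row, and 0 under the mandatory rule. The second plain-row re-start conflicts with the rule for values above 8x ULN only if the reappearance itself exceeds 8x ULN with no other reason found, or if a mandatory stop at the first event was missed. The conflict is therefore best stated at the first occurrence: 1 against 0.

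**5. Limits elsewhere in Section 8.4.3.** After a DLT in Cycle 1, dosing may be delayed only if the Grade 3 non-hematological toxicity lasts no more than 7 days. The lower dose level must have been evaluated during escalation. A subject at the starting dose is removed, and a third dose reduction is not allowed. These limits can bring the table's count down to 0 in a given subject, but they do not remove the conflict in general.

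**The case against.** The strongest reply is that the protocol can be read as consistent. The mandatory paragraph is in the same subsection, directly under the table, and its wording suggests a rule added on top of the graded schedule. Section 7.2.1 repeats it. On that reading, the table's options remain where another reason exists, and the stop applies where none does. Harm then requires a site to use the table without reading the next paragraph or the withdrawal criteria. This supports an override as the likely intent. It does not supply the override, and the row naming values above 8x ULN expressly offers resumption with no such condition. The footnotes attribute the stop criteria to Amendment 6 and point to Section 15.6.2.16. That section is not in the text available here, so the absence of a precedence rule is stated only for the text seen.

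A reader might also infer more than the documents support:

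- **That most events reaching the table meet the mandatory stop.** Possibly related and no other reason found are different thresholds. An event may have a plausible contributing cause that is not a clear alternative explanation. How often the rules collide cannot be derived.
- **That the table allows a re-start at every event.** It withdraws the subject at the second reappearance in the plain row and at the first in the other row.
- **That a liver safeguard is missing.** The correct rule is present in two places.

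**Conclusion.** The point holds as an internal contradiction that bears on subject safety. For a first, possibly related Grade 3 ALT/AST rise above 8x ULN with no other reason found, Table 8-6 permits one re-start at a reduced dose. This comes from the plain Grade 3 row, or from the row for values above 8x ULN if the hold option is chosen. The paragraph below the table and Section 7.2.1 permit none.

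The conclusion assumes that the general limits in Section 8.4.3 do not already bar re-treatment, and that no precedence rule stands in the part of the protocol not available here. The protocol states no event rate, so the number of subjects affected is unknown. Nothing in the text supports a claim that the MTD or a primary variable is affected. It should be corrected, because a stopping rule for liver injury should have only one reading.

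**What to change.** Make two changes to Table 8-6.

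1. Add one sentence stating that the mandatory discontinuation criteria override all rows. These are AST/ALT above 3x ULN with bilirubin above 2x ULN, AST/ALT above 8x ULN, and AST/ALT above 5x ULN for more than 2 weeks, each with no other reason found.
2. Add the condition *unless a mandatory discontinuation criterion is met* to the hold-and-resume instruction in both the plain Grade 3 row and the row for values above 8x ULN.

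The plain Grade 3 row should not be capped at 8x ULN, because an isolated value above that level with another identified reason would then have no row. The other row should not be limited to cases with another identified reason either. That could remove the hold option for hepatic failure without values above 8x ULN, which the mandatory criteria do not by themselves forbid. The shared condition avoids both problems.

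The cost is amendment wording: one sentence and one condition in each of two rows. No new data, visits or analyses are needed, and no option that the mandatory criteria leave open is lost.

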## **Increased Ca x PO451**

Dose modifications of BAY 1163877 for . Ca x PO4  $\geq$  70 mg²/dL² considered possibly related to BAY 1163877 are presented in Table 8-7.

<sup>50 Liver toxicity criteria amended by Amendment 6, see section 15.6.2.16

<sup>51 Section amended by Amendment 6, see section 15.6.2.16

No. BAY 1163877 / 16443

17 Oct 2018 Version 8.0 Page: 64 of 395

Table 8-7: Dose modifications of BAY 1163877 for Increased Ca x PO4 - amended

Toxicity	Modification schedule
Ca x PO4 (≥ 70 mg²/dL²)	Hold BAY 1163877, treat with phosphate chelators and check twice weekly until recovery, to Ca x PO4 < 70 mg²/dL².  Resume same dose level, continue phosphate chelators and check weekly for at least 4 weeks.
- 1 st reappearance	Hold BAY 1163877, treat with phosphate chelators and check twice weekly until recovery to Ca x PO4 < 70 mg²/dL², then reduce 1 dose level, continue phosphate chelator and check weekly for at least 4 weeks.
- 2 nd reappearance	Hold BAY 1163877 and check twice weekly until recovery to Ca x PO4 < 70 mg²/dL², then reduce 1 additional dose level, continue phosphate chelators and check weekly for at least 4 weeks.
- 3 rd reappearance	Withdraw subject from study treatment.

In patients with hyperphosphatemia (Ca x PO4  $\geq$  70 mg/dL), the serum phosphate and calcium levels have to be checked twice weekly until resolution (Ca x PO4  $\leq$  70 mg/dL).

In patients with hypocalcemia, an additional 12-lead ECG has to be obtained on the day of detection of hypocalcemia.

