## 8.4.3 Dose modification and delays - amended

Doses of study drug (BAY 1163877) may be delayed or reduced in case of clinically significant hematologic and other toxicities that are possibly, probably or definitely related to study drug therapy. Toxicities will be graded using the CTCAE v 4.03 (see Section 16.5).

No intra-subject dose escalation will be permitted. However, the dose can be reduced or delayed for an individual subject based on toxicities that are related to study drug.

If a subject experiences a DLT during Cycle 1, the next dose of BAY 1163877 can be delayed for up to 21 days, but only in cases Grade 3 non-hematological toxicities persist no longer than 7 days.

All subjects who are re-treated following a DLT should undergo dose reduction (see Table 8-3).

If the toxicity resolves to  $\leq$  Grade 1, the next dosing of BAY 1163877 at 1 dose level below the current dose (see Table 6-3) can be considered, provided that this dose level has been evaluated during the dose escalation part of the study. Detailed dose adjustments for hematological toxicities are described in Table 8-4. If the subject was dosed at the starting dose level, the subject should be removed from the study. If the toxicity fails to resolve to  $\leq$  Grade 1 within 21 days after the planned treatment date, the subject will be removed from the study. Subjects who experience a Grade 4 non-hematological toxicity will be removed from the study.

## Drug-related adverse events of $\geq$ Grade 3

For ≥ Grade 3 adverse event regarded as related to study drug, the next dosing of BAY 1163877 can be delayed for up to 21 days. If the toxicity fails to resolve to ≤ Grade 1 within 21 days after the scheduled dosing date, the subject will be removed from the study. If the toxicity resolves to ≤ Grade 1, the next dosing of BAY 1163877 at 1 dose level below the current dose (see Table 8-5) can be considered, provided that this dose level has been evaluated during the dose escalation part of the study. Dose adjustments for toxicities are detailed in Table 8-3.

If the re-treatment reproduces the same toxicity grade, the next dosing of BAY 1163877 can be delayed for up to 21 days until the toxicity has resolved to  $\leq$  Grade 1. Re-treatment is possible at 1 dose level below the previous dose.

No. BAY 1163877 / 16443

17 Oct 2018 Version 8.0 Page: 62 of 395

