Subjects who experience a Grade 4 non-hematological toxicity will be removed from the study. If more than 2 dose reductions are required, treatment will be permanently discontinued.

Table 8-3: Scheme for dose-level reduction of BAY 1163877 in subjects with solid tumors

Dose level	Action	
-1	1 dose below level of DLT occurrence a	
-2	2 doses below level of DLT occurence a	
-3	Discontinue study drug permanently	

a alternatively, treatment can be continued at an interim dose level with at least 3 subjects evaluated

Table 8-4: Hematological criteria for dose delay and dose modification

Grade a	ANC (10  /L)	Platelets (10  /L)	Dose delay	Dose modification
1 - 2	≥1.0	≥50	Treat as scheduled	No change
3	<1.0 - 0.5	<50 - 25	$Delay^b \ until \leq Grade \ 1$	Decrease 1 dose level c
4	<0.5	<25	$Delay^b \ until \leq Grade \ 1$	Decrease 1 dose level c

- a Applies to all kinds of hematological toxicities; ANC and platelet count displayed as examples.
- b If no recovery after 21 days delay, treatment will be permanently discontinued.
- c Dose will not be re-escalated to original dose level after reduction for toxicity. If more than 2 dose reductions are required, treatment will be discontinued.

Table 8-5: Non-hematological criteria for dose delay and dose modification

Grade	Dose delay	Dose modification
1 – 2	Treat as scheduled	No change
3	Delay b until ≤ Grade 1	Decrease 1 dose level c
4	Discontinue study drug permanently	Discontinue study drug permanently

- a Excludes alopecia. A maximum duration of 48 hours of Grade 3 nausea or vomiting will be allowed and not be considered DLT.
- b If no recovery after 21 days delay, treatment will be permanently discontinued.
- c Dose will not be re-escalated after dose reduction for toxicity. If more than 2 dose reductions are required, treatment will be permanently discontinued.

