## 8.4.4 Dose-limiting toxicity (DLT)

Adverse events which qualify as DLTs are causally related to study drug (while in turn not all related AEs are regarded as DLT). Dose-limiting toxicity will be defined as any of the following occurring during Cycle 1 of a dose level and regarded by the investigators and / or sponsor to be related to BAY 1163877. The CTCAE v 4.03 will be used to assess toxicities / adverse events (see Section 16.5).

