#### Non-hematological

- Non-hematologic Grade 3 or Grade 4 toxicity (nausea and vomiting only if refractory to anti-emetics; excluding alopecia). A maximum duration of 48 hours of Grade 3 nausea or vomiting will be allowed and not be considered DLT.
- Serum calcium (albumin-corrected) x phosphate product  $> 70 \text{ mg}^2/\text{dL}^2$  (5.6 mmol/L) despite the use of phosphate binders

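### Table 8-7 resumes the same dose after any first Ca x PO4 episode, with no exception for one that is a DLT, although section 8.4.3 calls for dose reduction after a DLT

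*Protocol*

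**What the plan says.** Three parts of the protocol bear on re-dosing after a raised calcium-phosphate product.

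- **Section 8.4.4 (DLT definition).** A DLT is a listed event "occurring during Cycle 1 of a dose level and regarded by the investigators" or the sponsor as drug-related. One listed non-hematological event is "Serum calcium (albumin-corrected) x phosphate product" above 70 mg²/dL² "despite the use of phosphate binders".
- **Section 8.4.3 (general rule after a DLT).** "All subjects who are re-treated following a DLT should undergo dose reduction". Table 8-3 sets the first step at "1 dose below level of DLT occurrence". For the lowest dose the rule is: "If the subject was dosed at the starting dose level, the subject should be removed from the study".
- **Section 8.4.3, Increased Ca x PO4, Table 8-7.** For a related product of 70 mg²/dL² or more, the first row holds the drug, gives chelators and orders twice-weekly checks until the product is below 70. It then says: "Resume same dose level, continue phosphate chelators and check weekly for at least 4 weeks". Reduction by one level begins only at the first reappearance.

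Section 8.4.4 specifies albumin-corrected calcium. Table 8-7 and the text around it do not.

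**The concern.** The first row of Table 8-7 is triggered by the product alone. It does not ask whether the subject is in Cycle 1, whether binders were already being taken, or whether the event has been classed as a DLT. Some events that fall in this row are therefore DLTs, and for those the same section gives two opposite instructions on the next dose.

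What is at stake is the individual subject's re-exposure in a first-in-human trial. A site that follows Table 8-7 gives the dose that produced the DLT again. A site that follows the general rule goes down one level, or takes a starting-dose subject off study. Both sites could say that they followed the protocol.

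**Working it through.** The plan states no figure here to reproduce. The check sets the rules of sections 8.4.3 and 8.4.4 side by side for each situation that can arise.

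| Situation (drug-related) | DLT by the binder criterion of 8.4.4? | 8.4.3 general rule | Table 8-7 | Agreement |
|---|---|---|---|---|
| 1. First Cycle 1 episode above 70, no binders yet, below 70 at the next check | No | Not triggered | Same dose | Consistent |
| 2. First Cycle 1 episode above 70, binders already in use | Yes | Reduce, or remove at starting dose | Same dose | **Conflict** |
| 3. First Cycle 1 episode, chelators started under the first row, still above 70 at a later check | Depends on how despite is read | Reduce or remove, if a DLT | Same dose | **Arguable conflict** |
| 4. Cycle 1 reappearance above 70 on binders | Yes | Reduce | Reduce one level | Same direction |
| 5. First episode after Cycle 1 | No (outside the window) | DLT rule not triggered | Same dose | Consistent |
| 6. Product exactly 70 | No (8.4.4 needs more than 70) | Not triggered | Same dose | Consistent |

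**Can situation 2 occur?** Yes. Section 8.9 lets the investigator give therapies judged necessary for the subject's welfare, and phosphate binders are not among the prohibited therapies in section 8.9.2. Section 9.4.4 describes raised phosphate as a dose-dependent effect seen in every animal species tested, so an investigator may start a binder before the product reaches 70. No section that I found prescribes prophylactic binders, so the situation depends on discretionary use.

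**Is the same-dose instruction a pattern in the section?** No. Table 8-4 decreases one level at Grade 3 or 4. Table 8-5 decreases one level at Grade 3 and discontinues at Grade 4. Table 8-6 reduces one level at the first Grade 3 liver event, with permanent discontinuation to be considered in the severe form, and withdraws at Grade 4. Only the first row of Table 8-7 can return a subject to the same dose after an event that is a DLT.

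**Albumin wording.** The product is calcium times phosphate, so the difference between the corrected and uncorrected product is the calcium difference times phosphate. The documents give no values for either. Assuming a gap of 0.5 mg/dL between measured and corrected calcium and a phosphate of 7 to 8 mg/dL:

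- 0.5 x 7 = 3.5 mg²/dL²
- 0.5 x 8 = 4.0 mg²/dL²

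Under these assumptions, one sample near 70 could be above the limit by one section and below it by the other.

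**The case against.** The best defence is that Table 8-7 already follows the logic of section 8.4.4. The first row is where chelators are introduced, and a return above the limit while on them is a reappearance, for which the table reduces the dose. On that reading the first row is for subjects not yet on binders, and the reappearance rows cover the DLT. This is probably what was intended, and it explains situations 1 and 4. However, the row does not say it is limited to subjects not on binders, so situation 2 remains.

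The defence is stronger for situation 3. The first row itself foresees an interval of recovery, and the text adds that "the serum phosphate and calcium levels have to be checked twice weekly until resolution". If every value above 70 in that interval were a DLT, the row could apply in Cycle 1 only to episodes that normalise before the next check. A value that is falling while the drug is on hold and chelators have just begun is not plainly a toxicity despite binders. A reader might count this case as a definite contradiction. The text does not settle it, and I treat it only as arguable.

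Section 8.4.4 (Miscellaneous) also lets investigator and sponsor discuss whether a laboratory finding without clear clinical correlation is a DLT needing dose reduction. That route is optional and does not name this product, so it does not resolve the conflict. The same heading allows a DLT when the investigator thinks a toxicity warrants withholding the drug. A reader might infer that every first-row episode is a DLT because the row orders a hold. That route rests on the investigator's judgment, and the inference would leave the specific binder criterion with little purpose.

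Finally, a toxicity-specific table may be meant to override a general rule worded with should. Table 8-6 already departs from the general text by accepting recovery to Grade 2 where that text asks for Grade 1 or lower. But no sentence states an order of precedence, and Table 8-6 still reduces the dose.

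**Conclusion.** The point stands as a minor one. For a first Cycle 1 episode above 70 mg²/dL² that arises on binders, sections 8.4.3 and 8.4.4 together call for reduction, and the first row of Table 8-7 calls for the same dose. Persistence above 70 after chelators are started is a possible second case. One of the four rows is affected, and the difference is one dose level. At the 100 mg/day starting dose it is removal against continued treatment. That branch is probably historical in this version, since section 6.2 already reports preliminary safety data and section 8.9.3 refers to 800 mg b.i.d.

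Three stronger readings are not supported.

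- **Number affected.** A reader might take the 20% in the MTD definition as a cap, 0.20 x 20 = 4 DLTs per 20 subjects, and apply a share to it. It is a target rate and not a limit on observed counts. With a true rate of 20% and 20 subjects, P(5 or more) = 1 - P(4 or fewer) is about 0.37. The documents give no basis for the share of DLTs due to this event, so the number cannot be estimated.
- **Effect on the MTD.** DLTs are counted by section 8.4.4 whatever dose follows, so DLT counts and the MTD rules do not change.
- **The limit at exactly 70.** The text below Table 8-7 shows resolution at 70 or less, and the table at below 70. The alkaline phosphatase limit likewise appears with different signs in the synopsis and in section 7.1.1.2, so this may be only a transcription difference. It would matter only at exactly 70, where the table is clear.

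**What to change.** Leave the DLT definition in section 8.4.4 as it is. In the first row of Table 8-7, directly after the instruction to resume the same dose level, add: *unless the event is a DLT under 8.4.4 (Cycle 1, albumin-corrected product > 70 mg²/dL² despite phosphate binders), in which case reduce 1 dose level per Table 8-3, or remove the subject if at the starting dose*. State in Table 8-7 that calcium is albumin-corrected, as in section 8.4.4.

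If the sponsor wants situation 3 settled too, one sentence can say whether a value still above 70 after chelators are started under the first row counts as despite binders. Because that could alter which events are classed as DLTs, it should follow the reading already applied in earlier cohorts.

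The main change costs one clause and one qualifying word. It adds no assessments, and DLT counts stay comparable with earlier cohorts.
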